7.2.3 Immediate Reporting of Adverse Events to the Sponsor

7.2.3.1 Serious Adverse Events

A serious adverse event is any adverse event occurring at any dose or during any use of Sponsor's product that:

- Results in death;
- Is life threatening;
- Results in persistent or significant disability/incapacity;
- Results in or prolongs an existing inpatient hospitalization;
- Is a congenital anomaly/birth defect;
- Is an other important medical event.

Note: In addition to the above criteria, adverse events meeting either of the below criteria, although not serious per ICH definition, are reportable to the Sponsor in the same timeframe as SAEs to meet certain local requirements. Therefore, these events are considered serious by the Sponsor for collection purposes.

- Is a cancer;
- Is associated with an overdose.

Refer to [Table 16](#) for additional details regarding each of the above criteria.

For the time period beginning when the consent form is signed until treatment allocation/randomization, any serious adverse event, or follow up to a serious adverse event, including death due to any cause, that occurs to any subject must be reported within 24 hours to the Sponsor if it causes the subject to be excluded from the trial, or is the result of a protocol-specified intervention, including but not limited to washout or discontinuation of usual therapy, diet, placebo treatment or a procedure.

For the time period beginning at treatment allocation/randomization through 14 days following cessation of treatment, any serious adverse event, or follow up to a serious adverse event, including death due to any cause, whether or not related to the Sponsor's product, must be reported within 24 hours to the Sponsor either by electronic media or paper. Electronic reporting procedures can be found in the EDC data entry guidelines. Paper reporting procedures can be found in the Investigator Trial File Binder (or equivalent).

Additionally, any serious adverse event, considered by an investigator who is a qualified physician to be related to the Sponsor's product that is brought to the attention of the investigator at any time outside of the time period specified in the previous paragraph also must be reported immediately to the Sponsor.

All subjects with serious adverse events must be followed up for outcome.

7.2.3.2 Events of Clinical Interest

Selected non-serious and serious adverse events are also known as Events of Clinical Interest (ECI) and must be reported to the Sponsor.

For the time period beginning when the consent form is signed until treatment allocation/randomization, any ECI, or follow up to an ECI, that occurs to any subject must be reported within 24 hours to the Sponsor if it causes the subject to be excluded from the trial, or is the result of a protocol-specified intervention, including but not limited to washout or discontinuation of usual therapy, diet, placebo treatment or a procedure.

For the time period beginning at treatment allocation/randomization through 14 days following cessation of treatment, any ECI, or follow up to an ECI, whether or not related to the Sponsor's product, must be reported within 24 hours to the Sponsor, either by electronic media or paper. Electronic reporting procedures can be found in the EDC data entry guidelines. Paper reporting procedures can be found in the Investigator Trial File Binder (or equivalent).

Events of clinical interest for this trial include:

1. an overdose of Sponsor's product, as defined in Section 7.2.1 - Definition of an Overdose for This Protocol and Reporting of Overdose to the Sponsor, that is not associated with clinical symptoms or abnormal laboratory results.
2. an elevated AST or ALT lab value that is greater than or equal to 3X the upper limit of normal and an elevated total bilirubin lab value that is greater than or equal to 2X the upper limit of normal and, at the same time, an alkaline phosphatase lab value that is less than 2X the upper limit of normal, as determined by way of protocol-specified laboratory testing or unscheduled laboratory testing.*

*Note: These criteria are based upon available regulatory guidance documents. The purpose of the criteria is to specify a threshold of abnormal hepatic tests that may require an additional evaluation for an underlying etiology. The trial site guidance for assessment and follow up of these criteria can be found in the Investigator Trial File Binder (or equivalent).

3. a confirmed (i.e., verified by repeat testing) elevated AST or ALT laboratory value that is greater than or equal to 5 X ULN as a result of within-protocol-specific testing or unscheduled testing.

NOTE: In subjects with pre-existing elevations in transaminase values, only a further elevation that is not anticipated from an underlying medical condition will be considered an ECI. These events may require an additional evaluation for an underlying etiology. The trial site guidance for assessment and follow up of these criteria can be found in the Investigator Trial File Binder.

7.2.4 Evaluating Adverse Events

An investigator who is a qualified physician will evaluate all adverse events with respect to the elements outlined in [Table 16](#). The investigator's assessment of causality is required for each adverse event. Refer to [Table 16](#) for instructions in evaluating adverse events.

Table 16 Evaluating Adverse Events

Maximum Intensity	Mild	awareness of sign or symptom, but easily tolerated (for pediatric trials, awareness of symptom, but easily tolerated)
	Moderate	discomfort enough to cause interference with usual activity (for pediatric trials, definitely acting like something is wrong)
	Severe	incapacitating with inability to work or do usual activity (for pediatric trials, extremely distressed or unable to do usual activities)
 Seriousness	A serious adverse event (AE) is any adverse event occurring at any dose or during any use of Sponsor's product that:	
	† Results in death ; or	
	† Is life threatening ; or places the subject, in the view of the investigator, at immediate risk of death from the event as it occurred [Note: This does not include an adverse event that, had it occurred in a more severe form, might have caused death.]; or	
	† Results in a persistent or significant disability/incapacity (substantial disruption of one's ability to conduct normal life functions); or	
	† Results in or prolongs an existing inpatient hospitalization (hospitalization is defined as an inpatient admission, regardless of length of stay, even if the hospitalization is a precautionary measure for continued observation. (Note: Hospitalization for an elective procedure to treat a pre-existing condition that has not worsened is not a serious adverse event. A pre-existing condition is a clinical condition that is diagnosed prior to the use of a Merck product and is documented in the patient's medical history.); or	
	† Is a congenital anomaly/birth defect (in offspring of subject taking the product regardless of time to diagnosis); or	
	Is a cancer (although not serious per ICH definition, is reportable to the Sponsor within 24 hours to meet certain local requirements); or	
	Is associated with an overdose (whether accidental or intentional). Any adverse event associated with an overdose is considered a serious adverse event for collection purposes. An overdose that is not associated with an adverse event is considered a non-serious event of clinical interest and must be reported within 24 hours.	
	Other important medical events that may not result in death, not be life threatening, or not require hospitalization may be considered a serious adverse event when, based upon appropriate medical judgment, the event may jeopardize the subject and may require medical or surgical intervention to prevent one of the outcomes listed previously (designated above by a †).	
Duration	Record the start and stop dates of the adverse event. If less than 1 day, indicate the appropriate length of time and units	
Action taken	Did the adverse event cause the Sponsor's product to be discontinued?	
Relationship to Sponsor's Product	Did the Sponsor's product cause the adverse event? The determination of the likelihood that the Sponsor's product caused the adverse event will be provided by an investigator who is a qualified physician. The investigator's signed/dated initials on the source document or worksheet that supports the causality noted on the AE form, ensures that a medically qualified assessment of causality was done. This initialed document must be retained for the required regulatory time frame. The criteria below are intended as reference guidelines to assist the investigator in assessing the likelihood of a relationship between the test drug and the adverse event based upon the available information The following components are to be used to assess the relationship between the Sponsor's product and the AE ; the greater the correlation with the components and their respective elements (in number and/or intensity), the more likely the Sponsor's product caused the adverse event:	
	Exposure	Is there evidence that the subject was actually exposed to the Sponsor's product such as: reliable history, acceptable compliance assessment (pill count, diary, etc.), expected pharmacologic effect, or measurement of drug/metabolite in bodily specimen?
	Time Course	Did the AE follow in a reasonable temporal sequence from administration of the Sponsor's product? Is the time of onset of the AE compatible with a drug-induced effect (applies to trials with investigational medicinal product)?
	Likely Cause	Is the AE not reasonably explained by another etiology such as underlying disease, other drug(s)/vaccine(s), or other host or environmental factors

Relationship to Sponsor's Product (continued)	The following components are to be used to assess the relationship between the Sponsor's product and the AE: (continued)	
	Dechallenge	Was the Sponsor's product discontinued or dose/exposure/frequency reduced? If yes, did the AE resolve or improve? If yes, this is a positive dechallenge. If no, this is a negative dechallenge. (Note: This criterion is not applicable if: (1) the AE resulted in death or permanent disability; (2) the AE resolved/improved despite continuation of the Sponsor's product; (3) the trial is a single-dose drug trial); or (4) Sponsor's product(s) is/are only used one time.)
	Rechallenge	Was the subject re-exposed to the Sponsor's product in this trial? If yes, did the AE recur or worsen? If yes, this is a positive rechallenge. If no, this is a negative rechallenge. (Note: This criterion is not applicable if: (1) the initial AE resulted in death or permanent disability, or (2) the trial is a single-dose drug trial); or (3) Sponsor's product(s) is/are used only one time.) NOTE: IF A RECHALLENGE IS PLANNED FOR AN ADVERSE EVENT WHICH WAS SERIOUS AND WHICH MAY HAVE BEEN CAUSED BY THE SPONSOR'S PRODUCT, OR IF RE-EXPOSURE TO THE SPONSOR'S PRODUCT POSES ADDITIONAL POTENTIAL SIGNIFICANT RISK TO THE SUBJECT THEN THE RECHALLENGE MUST BE APPROVED IN ADVANCE BY THE SPONSOR CLINICAL DIRECTOR AND THE INSTITUTIONAL REVIEW BOARD/INDEPENDENT ETHICS COMMITTEE.
Consistency with Trial Treatment Profile	Is the clinical/pathological presentation of the AE consistent with previous knowledge regarding the Sponsor's product or drug class pharmacology or toxicology?	
The assessment of relationship will be reported on the case report forms /worksheets by an investigator who is a qualified physician according to his/her best clinical judgment, including consideration of the above elements.		
Record one of the following:	Use the following scale of criteria as guidance (not all criteria must be present to be indicative of a Sponsor's product relationship).	
Yes, there is a reasonable possibility of Sponsor's product relationship.	There is evidence of exposure to the Sponsor's product. The temporal sequence of the AE onset relative to the administration of the Sponsor's product is reasonable. The AE is more likely explained by the Sponsor's product than by another cause.	
No, there is not a reasonable possibility of Sponsor's product relationship	Subject did not receive the Sponsor's product OR temporal sequence of the AE onset relative to administration of the Sponsor's product is not reasonable OR the AE is more likely explained by another cause than the Sponsor's product. (Also entered for a subject with overdose without an associated AE.)	

7.2.5 Sponsor Responsibility for Reporting Adverse Events

All Adverse Events will be reported to regulatory authorities, IRB/IECs and investigators in accordance with all applicable global laws and regulations, i.e., per ICH Topic E6 (R1) Guidelines for Good Clinical Practice.

8.0 STATISTICAL ANALYSIS PLAN

This section outlines the statistical analysis strategy and procedures for the study. Changes to the analyses made after the protocol has been finalized, but prior to the database lock, will be documented in a supplemental SAP (sSAP) and referenced in the Clinical Study Report (CSR) for the study. Post hoc exploratory analyses will be clearly identified in the CSR.

8.1 Statistical Analysis Plan Summary

Key elements of the statistical analysis plan are summarized below; the comprehensive plan is provided in Sections 8.2-8.12.

Study Design Overview	A non-randomized, non-controlled, open-label trial of IMI/REL in subjects with cIAI or cUTI.
Treatment Assignment	All enrolled subjects will receive IV study therapy of IMI/REL in an open-label manner.
Analysis Populations	Safety All Subjects as Treated (ASaT) population Efficacy Modified intention to treat (MITT) population and microbiologically-evaluable (ME) population; ME population will serve as the primary analysis population
Primary Endpoint(s)	Safety Safety parameters including adverse events (AEs), pre-defined limits of change (PDLCs), change from baseline in vital signs and laboratory tests Efficacy 1. Proportion of subjects with cIAI achieving favorable clinical response to IMI/REL at the EOT visit 2. Proportion of subjects with cUTI achieving favorable microbiological response to IMI/REL at the EOT visit
Secondary Endpoints	1. Proportion of subjects with cIAI achieving favorable clinical response to IMI/REL at the TOC visit 2. Proportion of subjects with cUTI achieving favorable microbiological response to IMI/REL at the TOC visit
Statistical Methods for Key Safety Analyses	AEs and PDLCs will be summarized by numbers and percentages of subjects. For broad clinical and laboratory AE category, 95% confidence intervals (CIs) based on the method of Agresti and Coull will be calculated for the proportion of subjects. Change from baseline in vital signs and laboratory tests will be calculated by visit.
Statistical Methods for Key Efficacy Analyses	A 95% CI based on the method of Agresti and Coull will be provided for the proportion of subjects with cIAI achieving favorable clinical response to IMI/REL at the EOT visit. The same analysis will be performed for the proportion of subjects with cUTI achieving favorable microbiological response to IMI/REL at the EOT visit. The same measures at the TOC visit will also be analyzed in the same manner.

Interim Analyses	No interim analysis is planned.
Multiplicity	No multiplicity adjustment is planned.
Sample Size and Power	
A total of 80 subjects will be enrolled.
 
For an AE or a specific safety event of interest, if the underlying incidence is 2%, then there is 80% chance that it is observed in at least one subject among the 80 subjects enrolled.
 
In each of the cIAI and cUTI cohorts, if 40 subjects are enrolled, 28 subjects are included in the ME population and evaluable at the EOT visit, and 26 subjects achieve favorable response, then the estimated percentage and corresponding 95% CI of subjects achieving favorable response will be 92.9% (76.3%, 99.1%).

8.2 Responsibility for Analyses/In-House Blinding

The statistical analysis of the data obtained from this study will be the responsibility of the Clinical Biostatistics department of the SPONSOR. This trial is being conducted as a non-randomized, open-label study, i.e., subjects, investigators, and SPONSOR personnel will be aware of subject treatment assignments after each subject is enrolled and treatment is assigned.

8.3 Hypotheses/Estimation

The objectives of the study are stated in Section 3.

8.4 Analysis Endpoints

8.4.1 Safety Endpoints

A description of safety measures is provided in Section 4.2.3.1. Safety endpoints will include AEs, PDLCs, and change from baseline in vital signs and laboratory tests. The baseline value is defined as the last available measurement prior to the start of the IV study therapy, which typically corresponds to the value obtained at Visit 2.

8.4.2 Efficacy Endpoints

A full description of the efficacy measures is provided in Section 4.2.3.2. The definition of favorable clinical and by-pathogen microbiological responses at each visit is summarized in [Table 17](#). A favorable overall microbiological response for a subject at a particular visit requires favorable responses in all baseline pathogens at that visit.

Table 17 Definition of favorable clinical and microbiological responses by visit

Visit	Rating(s) considered a favorable response	
	Clinical	Microbiological [†] (by-pathogen)
EOT	“cure” or “improved”	“eradication” or “presumptive eradication” [‡]
TOC	“cure”	“sustained eradication” or “presumptive eradication” [‡]

[†] A favorable overall microbiological response for a subject at a particular visit requires favorable responses in all baseline pathogens at that visit.
[‡] cIAI only

8.5 Analysis Populations

8.5.1 Safety Analysis Population

The ASaT population will be used for the analysis of safety data in this study. The ASaT population consists of all enrolled subjects who receive at least one dose of IV study therapy.

At least one laboratory or vital sign measurement obtained subsequent to at least one dose of IV study therapy is required for inclusion in the analysis of each specific parameter. To assess change from baseline, a baseline measurement is also required.

8.5.2 Efficacy Analysis Population

Two populations, the MITT and the ME populations, will be used for the analysis of efficacy data in this study. The ME population will serve as the primary population for efficacy analyses in this study.

The MITT population is defined as all enrolled subjects who receive at least one dose of IV study therapy. In this study, this is identical with the ASaT population. The ME population is a subset of the MITT population that excludes subjects due to major deviations from the protocol that may substantially affect the results of the efficacy analyses. Potential deviations that may result in the exclusion of a subject from the ME population include the following:

1. The subject fails to meet the protocol definition of cIAI or cUTI
2. The subject had significant violations of inclusion/exclusion criteria that could impact the efficacy assessment (e.g., receipt of previous or concurrent systemic antibacterial therapy beyond those allowed per protocol)
3. The subject received less than 96 hours of IV study therapy (16 infusions)
4. (cIAI only) The subject's pre-study/post-operative culture from the site of infection fails to grow at least 1 gram-negative enteric(s) and/or anaerobic pathogen(s) commonly isolated in IAI. (Note: Subjects who fail to grow a single gram-negative enteric and/or anaerobic pathogen from the site of infection are excluded from the ME population. That is, subjects with only gram-positive pathogens identified will be excluded, as well as those who do not grow any pathogens.)

(cUTI only) The subject's pre-study urine culture fails to grow at least 1 gram-negative and/or anaerobic, pathogen at sufficient quantity specified in the inclusion criteria (See Section 5.1.2 for details)

The composition of the ME population at each time point of interest will be made prior to the database lock and will be documented in a separate memo.

Details on the approach to handling missing data are provided in Section 8.6.

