5.2.3 Trial Blinding

This is an open-label trial; therefore, the Sponsor, investigator and subject will know the treatment administered.

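### Section 8.5.2 leaves part of the primary ME population to judgement (criterion 2 and an open list), and nothing in the plan keeps EOT and TOC responses from those who decide it

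*Combined protocol and SAP*

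**What the plan says.** Section 8.5.2 states: "The ME population will serve as the primary population for efficacy analyses in this study". ME is the set of treated subjects less those with major deviations, and the exclusion rule opens with "Potential deviations that may result in the exclusion of a subject from the ME population include the following". Four criteria follow:

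- Criterion 1: the subject does not meet the protocol definition of cIAI or cUTI.
- Criterion 2: "The subject had significant violations of inclusion/exclusion criteria that could impact the efficacy assessment". One example is given, antibacterial therapy outside what the protocol allows.
- Criterion 3: fewer than 96 hours of study drug (16 infusions).
- Criterion 4: no qualifying baseline pathogen. For cIAI the note is mandatory: "Subjects who fail to grow a single gram-negative enteric and/or anaerobic pathogen from the site of infection are excluded from the ME population". For cUTI the quantity is tied to the colony counts in Section 5.1.2.

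On timing, the section says: "The composition of the ME population at each time point of interest will be made prior to the database lock". The result is documented in a separate memo.

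Section 5.2.3 adds: "This is an open-label trial; therefore, the Sponsor, investigator and subject will know the treatment administered". Under Section 4.2.3.2.1.1 the investigator rates clinical response at EOT and TOC and records it on the eCRF. Under Section 4.2.3.2.1.2.3 and the notes to the Section 6.0 flow chart, the Sponsor determines overall microbiological response. Section 8.2 makes the Sponsor's biostatistics department responsible for the analysis. Section 8.6.2 plans a supportive MITT analysis of all treated subjects, with missing or indeterminate responses counted as failures.

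**The concern.** A population memo signed before lock guards against selection when those who sign it cannot link exclusions to results. That protection is weak here. There is one open-label arm, responses are recorded as the trial proceeds, and the Sponsor itself derives the cUTI primary outcome. Membership is set separately for each time point, and criteria 2 and 3 can turn on events after treatment starts. No section requires the decision to be made without knowledge of response.

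With about 28 evaluable subjects per cohort and few failures expected, each classification of a failure matters. There is no comparator arm in which the same selection could cancel. What is at stake is the accuracy of the two primary proportions and their intervals.

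**Working it through.** **Inputs.** Section 8.9 and Table 19: 40 enrolled per cohort, at least 70% in ME (0.70 × 40 = 28), 26 favorable, Agresti-Coull 95% intervals.

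**Formula.** With z = 1.96, ñ = n + z² and p̃ = (x + z²/2)/ñ. The interval is p̃ ± z√(p̃(1 − p̃)/ñ), cut off at 100%.

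**The plan's own figure.** For x = 26 and n = 28: ñ = 31.84, p̃ = 27.92/31.84 = 0.877, half-width 0.114. The interval is 76.3% to 99.1% around 92.9%, as stated in Section 8.9. All eight rows of Table 19 reproduce to 0.1 point.

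**Excluding failures from the planning case.**

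| Case | Estimate (95% CI) | Shift in estimate | Shift in lower limit |
|---|---|---|---|
| 26/28, as planned | 92.9% (76.3, 99.1) | – | – |
| 26/27, one failure out | 96.3% (80.2, 100.0) | +3.4 | +3.9 |
| 26/26, both out | 100% (84.8, 100.0) | +7.1 | +8.5 |

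**Excluding a responder instead.** 25/27 = 92.6%, a shift of −0.3 points. With high response rates the estimate is far more sensitive to how failures are classified than to how responders are.

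**Range over Table 19.** One failure excluded moves the estimate by 2.7 points (32/35 = 91.4% to 32/34 = 94.1%) up to 4.8 points (20/21 = 95.2% to 20/20 = 100%). Two move it by 5.5 points (32/35 to 32/33 = 97.0%) up to 9.5 points (19/21 = 90.5% to 19/19 = 100%).

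**Can MITT expose the effect?** MITT brings back all 12 of the 40 subjects outside the 28, whatever the reason. If their outcomes are unknown (an assumption), MITT lies anywhere from 26/40 = 65% to 38/40 = 95%. A gap between ME and MITT could come from subjects without a qualifying pathogen, from indeterminate responses counted as failures, or from judgement-based exclusions. The two figures do not tell these apart.

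**Sections 8.5.2 and 8.6.2 side by side.** In the ME analyses, Section 8.6.2 counts subjects who stop study drug for lack of efficacy as clinical failures and as presumed persistence. Criterion 3 in Section 8.5.2 makes no exception for them. A failure who stops before 16 infusions may therefore be kept or dropped under the present wording. Making the list mandatory without reconciling the two sections would drop every such failure.

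**The case against.** Much of the ME definition is not discretionary. The cIAI culture exclusion is mandatory, and Section 4.2.3.2.1.2.1 repeats it. The cUTI culture rule and criterion 3 have numeric cut-offs, and criterion 1 refers to a written definition. That stands, and it confines the problem to criterion 2 and the open list.

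A reader might infer that the whole 30% outside ME is open to choice. The documents do not support this. Section 8.9 says at least 70% will be in ME, so 30% is an upper figure, and no breakdown by reason is given. Section 5.1.2 lets cUTI subjects enrol before urine culture results are known, so rule-based culture exclusions could account for much of it.

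A reader might also infer that membership will be settled after responses have been seen. Section 8.5.2 sets only a latest date. The open-label statement in Section 8.2 concerns treatment assignment, not who sees responses when ME is decided. The text supports no more than that membership can be settled with responses visible.

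Finally, MITT is prespecified for all four primary and secondary efficacy endpoints. It is a visible check on the result, although it does not govern the exclusion decisions or isolate their effect.

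**Conclusion.** The point holds in limited form. The primary population has an open, permissive exclusion rule with one judgement-based criterion, and no stated safeguard separates that judgement from the responses. In the planning case, excluding one failure adds 3.4 points and excluding two adds 7.1. Over Table 19, one exclusion adds 2.7 to 4.8 points.

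These are illustrations. They assume that the excluded subjects are failures, and nothing in the documents says that any would be removed or suggests intent to do so.

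Two stronger readings do not follow. The trial estimates proportions without an efficacy hypothesis or success threshold, so the harm is a possibly biased estimate and interval, not an inflated type I error. Nor does a single exclusion exceed the spread between arms in the Phase II cIAI trial: 98.8% − 95.2% = 3.6 points, against 3.4 here. This is a worthwhile, low-cost improvement and not a fatal flaw.

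**What to change.** Amend Section 8.5.2, or the supplemental SAP before any response data are reviewed, as follows:

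1. Close the list with mandatory wording: a subject leaves ME when a listed criterion applies, and for no other reason.
2. Reconcile criterion 3 with Section 8.6.2, so that a subject who stops for lack of efficacy before 16 infusions stays in ME as a failure. This must accompany step 1; otherwise the closed list removes early failures automatically.
3. Derive criteria 3 and 4 by program from dosing records, discontinuation reason and baseline culture.
4. Decide criteria 1 and 2 from listings that omit EOT and TOC ratings, follow-up cultures and antibiotics started for treatment failure. The last item matters because Section 8.6.2 ties lack of efficacy to later non-study antibiotics, so a full concomitant-medication listing would often reveal failures. Sign the memo on that basis.
5. Report the ME estimate with criterion 1 and 2 exclusions added back as a sensitivity analysis. For scale, adding one failure back to 26/28 gives 26/29 = 89.7% (72.8, 97.2).

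The cost is SAP wording, restricted listings and one extra analysis per endpoint. No patients or visits are added. The downside is less freedom to judge unusual deviations case by case.
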